The probe will be used in direct contact with the cardiac tissue with a pressure of approximately 0.7 mmHg, which is less than 1% of diastolic blood pressure. The maximum laser energy that the system is capable of delivering is 15 mW at 480 nm. This power and wavelength has been approved by the FDA for direct in-vivo imaging for various body tissues, including gastrointestinal, urogenital, and pulmonary. The proposed application is approximately 80% less than the maximum allowable retinal exposure, according to the IEC 60825-1 standard.

(4) Definition of Primary and Secondary Outcomes/Endpoints

Primary Outcome: All adverse events will be collected and relatedness to study participation will be determined. Complications will be compared to average complication rates for ASD repairs.

Hypothesis: Subjects will not experience a higher rate of adverse events than is expected in a clinical setting (<3-4% for all types of adverse events).

Secondary Outcome: The logistical feasibility of conducting FCM imaging during cardiac surgery.

Hypothesis: The study procedure will be logistically feasible in terms of added time on bypass and the ability to incorporate FCM imaging into standard cardiac surgery OR procedures. The rate of enrollment will be evaluated separately.

Secondary Outcome: The quality of the FCM image files collected, defined as the ability of observers to distinguish features and discriminate between working myocardium and nodal tissue.

Hypothesis: Blinded raters will be able to use the FCM image files to distinguish features and discriminate between working myocardium and nodal tissue.

(5) Data Collection Methods, Assessments, Interventions and Schedule (what assessments performed, how often)

Standardized demographic and clinical assessments of all study participants will be performed via medical record review prior to and after surgery until the subject is discharged from the hospital. Images will be obtained during surgery and saved using Cellvizio Software and Viewer. The image files will be de-identified and provided to blinded raters for analysis. Medical records of enrolled subjects will be reviewed post-surgery while the subject is inpatient in the hospital. Adverse events will be abstracted from the record and recorded on a CRF and input into an InForm database.

(6) Study Timeline

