1. Death. This includes any death that occurs during the conduct of a clinical study, including deaths that appear to be completely unrelated to the test drug (e.g., a car accident). If a study subject dies during the study and an autopsy is performed, the autopsy results will be attached to the study subject's Case Report Form (CRF). Possible evidence of organ toxicity and the potential relationship of the toxicity to the test drug are of particular interest. The autopsy report should distinguish the relationship between the underlying diseases, their side effects, and the cause of death.
2. Life-threatening adverse drug experience. This includes any AE during which the study subject is, in the view of the investigator, at immediate risk of death from the reaction as it occurred. This definition does not include any event that may have caused death if it had occurred in a more serious form. For example, drug-induced hepatitis that resolved without evidence of hepatic failure would not be considered a life-threatening event, even though drug-induced hepatitis can be fatal.
3. Persistent or significant disability or incapacity or substantial disruption of the ability to conduct normal life functions.
4. Inpatient hospitalization or prolongation of existing hospitalization, except for admission for elective surgery.
5. Important medical event that may not result in one of the above outcomes, but may jeopardize the health of the study subject or require medical or surgical intervention to prevent one of the outcomes listed in the above definition of serious event.

(4) Definition of Unexpected Adverse Events

An adverse event is "unexpected" when its nature (specificity) or severity is not consistent with applicable product information, such as safety information provided in the package insert, the investigational plan, the investigator's brochure or the protocol.

In addition, an adverse event is "unexpected" when not one of the most common complications that typically arise post-operation for ASD repair such as: rhythm disturbances, arrhythmia, pericarditis, cardiac tamponade, bleeding, residual holes requiring a re-operation, transfusion associated diseases, stroke, and brain damage. These adverse events will be considered expected and unrelated to the study drug.

(5) Toxicity Grading

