We will assign toxicity grades to indicate the severity of adverse experiences and toxicities. Toxicity grading consistent with NCI-CTCAE v 4.03 will be used for this protocol. The purpose of using the NCI-CTCAE system is to provide standard language to describe toxicities and to facilitate tabulation and analysis of the data and assessment of the clinical significance of treatment-related toxicities.

Adverse events not included in the NCI-CTCAE listing will be recorded and graded 1 to 5 according to the General Grade Definition provided below:

Grade 1	Mild	Transient or mild discomforts (< 48 hours), no or minimal medical intervention/therapy required, hospitalization not necessary (non-prescription or single-use prescription therapy may be employed to relieve symptoms, e.g., aspirin for simple headache, acetaminophen for post-surgical pain).
Grade 2	Moderate	Mild to moderate limitation in activity, some assistance may be needed; no or minimal intervention/therapy required, hospitalization possible.
Grade 3	Severe	Marked limitation in activity, some assistance usually required; medical intervention/therapy required, hospitalization possible.
Grade 4	Life-threatening	Extreme limitation in activity, significant assistance required; significant medical/therapy intervention required, hospitalization, or hospice care probable.
Grade 5	Death	Death

For additional information and a printable version of the NCI-CTCAE v. 4.03 manual, consult the NCI-CTCAE website, <http://ctep.cancer.gov/reporting/ctc.html>.

(6) Guidelines for Determining Causality of an Adverse Event

The Investigator will use the following question when assessing causality of an adverse event to study drug: Is there a reasonable possibility that the drug caused the event? An affirmative answer designates the event as a suspected adverse reaction.

If there is any doubt as to whether a clinical observation is an AE, the event should be reported. All AEs must have their relationship to study product assessed using the terms related or not related. In a clinical trial, the study product must always be suspect. To help assess, the following guidelines are used:

- Related – Related means there is evidence to show a causal relationship between the study product and the adverse event.

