- Possibly Related – There is a reasonable possibility that the study product caused the adverse event. Reasonable possibility means that there is evidence to suggest a causal relationship between the study product and the adverse event.

Specific adverse events considered related or possibly related to study participation have been identified as: myocarditis or ventricular dysfunction, as measured by ejection fraction and fractional shortening. These will be reported to the FDA in an IND Safety Report, per discussion with the FDA.

Specific ECG and rhythm abnormalities requiring DSMB review prior to enrollment of next patient:

1. AV block > the a PR interval > 220 msec lasting more than 2 hours post completion of cardiopulmonary bypass. This does not include transient Wenkebach with sleep/rest/hypothermia.
2. Need for atrial pacing or junctional rhythm lasting more than 6 hours post completion
3. Hypotension or ventricular dysfunction requiring pressor support > 5mcg/kg/min of dopamine more than 4 hours post completion of cardiopulmonary bypass.

- Not Related – There is not a reasonable possibility that the administration of the study product caused the event, and/or there is a more plausible explanation for the adverse event than administration of the study product.

(7) Recording and Reporting Procedures

Reporting Adverse Events and Serious Adverse Events

All AEs will be followed until the time the event is resolved or medically stable, or until subject is discharged from hospital, whichever comes first. AEs may be discovered through any of these methods:

- Observing the subject
- Questioning the subject, which should be done in an objective manner
- Receiving an unsolicited complaint from the subject
- Review of medical records/source documents

All AEs must be recorded accurately on the Adverse Event log for each study subject. The date of onset and duration of the AE, grade, whether it was expected or unexpected, action taken, date of resolution (if applicable) and outcome of the event must be recorded. The investigator will treat subjects experiencing adverse events appropriately and observe them at suitable intervals until their symptoms resolve or their status stabilizes or they are discharged from the hospital.

SAEs and unexpected problems will be reported promptly to BCH IRB according to local regulations and guidelines.

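### The primary outcome asks for relatedness to study participation, but E(6) rates it against the drug or an undefined study product, and E(4) pre-declares common complications unrelated

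*Protocol*

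**What the plan says.** The primary outcome in D(4) collects all adverse events and states that "relatedness to study participation will be determined". It also compares complications with average rates for ASD repair.

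Participation consists of more than the dye. D(1) adds about 90 seconds of direct probe contact and about 3 minutes on bypass. D(3.2) describes a laser of up to 15 mW at 480 nm.

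E(6) gives the causality rule. Its guiding question is: "Is there a reasonable possibility that the drug caused the event". It then says: "All AEs must have their relationship to study product assessed using the terms related or not related", and adds: "In a clinical trial, the study product must always be suspect". Three ratings follow (Related, Possibly Related, Not Related), each worded in terms of the study product. Not Related applies if there is no reasonable possibility that giving the product caused the event, and/or if "there is a more plausible explanation for the adverse event than administration of the study product". The same section has one wider statement: "Specific adverse events considered related or possibly related to study participation have been identified as: myocarditis or ventricular dysfunction".

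E(4) gives an open list of common complications after ASD repair, including rhythm disturbances and arrhythmia, and concludes: "These adverse events will be considered expected and unrelated to the study drug".

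E(7) sends all SAEs to the DSMB chair and has the panel judge how an SAE relates to the underlying disease. E(8) bases expedited reporting on whether a serious, unexpected event is associated with the Study Agent/Intervention.

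**The concern.** Safety is the primary aim and only six subjects are planned, so the attribution of each event carries much of the safety conclusion. The outcome asks whether taking part caused the event. The rating rule asks whether the drug or the study product did. If those differ, harm from the imaging device or the added procedure can be recorded as unrelated in the analysis meant to detect it.

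The E(4) statement raises a second problem. ASD repair was chosen because it exposes the conduction system for imaging (D(2)), and the probe is placed directly on cardiac tissue. Rhythm disturbances are therefore a class of event for which attribution matters, yet E(4) appears to settle it before any case is seen. That an event is expected after surgery does not show that it is unrelated to what the study added.

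**Working it through.** No arithmetic applies, because the protocol states no proportion of related events. The check sets the passages side by side and applies the definitions.

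**Step 1: the object of causality.**
- D(4): study participation.
- E(6), guiding question: the drug. E(6), all ratings: the study product.
- E(6), named events: study participation, for 2 event types (myocarditis, ventricular dysfunction).
- E(8): Study Agent/Intervention, for serious events only.

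Counting drug and study product as one, that makes three study-side objects. Of the 3 rating definitions, 3 refer to the study product and 0 name the probe, the laser or bypass time.

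**Step 2: what study product means.** The term appears only in E(6) and is not defined. Four features point to the dye:
- E(6) opens with causality to the study drug.
- Not Related speaks of administration.
- D(3) lists the agent and the device under separate headings.
- Section K words drug administration apart from image acquisition.

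Stretching the term to include the device would still leave out the extra bypass time, which is not a product that is administered.

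**Step 3: apply the ratings.** Take a hypothetical surface injury at the imaging site, best explained by probe contact. It is neither myocarditis nor ventricular dysfunction.
- Under D(4) it is related to participation.
- Under E(6), read as the dye, a better explanation than the dye exists. The second limb of Not Related is met, and the and/or wording makes that limb sufficient.
- Dye and probe are applied in the same operative step, so the dye may remain a reasonable possibility. Possibly Related can then be met too.

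The definitions therefore permit Not Related without compelling it, and two investigators could rate the same event differently.

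**Step 4: E(4) against E(6).** E(6) requires a rating for every event and holds the product always suspect. E(4) assigns a class of events to unrelated without case review. Both cannot govern, and nothing says which does.

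**Step 5: what depends on the rating.**
- The D(4) hypothesis and rate comparison use all adverse events: no.
- SAE notice to the DSMB chair: no.
- The list headed "Specific ECG and rhythm abnormalities requiring DSMB review prior to enrollment of next patient", which covers AV block, pacing or junctional rhythm, and hypotension or ventricular dysfunction needing pressor support: no.
- Relatedness in the primary outcome: yes.
- E(8): yes, if its associated/not-associated split uses the E(6) rating. The listed E(4) complications count as expected, so they fall outside its expedited route whatever their rating.

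**Step 6: where the rating is recorded.** The fields E(7) lists for the adverse event log cover onset, duration, grade, expectedness, action, resolution and outcome. Relatedness is not among them.

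**The case against.** The strongest reply is that the effect is small. The study is descriptive, every event is logged whatever its rating, and the DSMB routes work without it. That stands: events may be misclassified but are not lost.

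A second reply is that the primary aim in section A names only fluorescein, which a drug-based scale serves. Narrowing D(4) to the dye would also remove the mismatch. It would, but D(1) sets out to assess the safety of using confocal microscopy, which favours the wider object. In any case, the aim does not reconcile E(6) with D(4) as written.

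Third, E(8) already uses an object wider than the agent. This is a partial answer, so a reader should not infer that nothing in the protocol looks beyond the drug. But the term is undefined, covers serious events only and comes with no decision rule. The DSMB's judgement in E(7) concerns the underlying disease and does not fill the gap.

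Fourth, the difference between two required terms and three defined ones is minor. The guiding question and Possibly Related both turn on a reasonable possibility, and the first limb of Not Related negates it, so a binary split can be recovered.

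**Conclusion.** The inconsistency is real and should be corrected. D(4) and E(6) use different objects of causality, and E(4) contradicts the requirement in E(6) to assess every event. The first consequence assumes that study product means the dye, which is the natural reading but not a stated one.

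Two stronger conclusions are tempting, and the protocol does not support them. A reader might infer that the common complications are never assessed for a link to the dye. A contradiction between E(4) and E(6) leaves it unclear whether they are assessed; it does not establish that they are not. A reader might also infer that any harm from probe, laser or bypass time must be rated Not Related. The overlap with Possibly Related, and the two event types tied to participation, rule that out.

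No numeric effect on an endpoint is claimed. The effect is limited to the relatedness part of the primary outcome and, if E(8) relies on the same rating, to regulatory reporting.

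**What to change.** - **E(6):** rate relatedness to any study intervention, meaning the dye, the imaging device, or the study procedure including added bypass time. Limit Not Related to events with a more plausible explanation other than any study intervention.
- **E(4):** keep the listed complications as expected, but delete the words declaring them unrelated to the study drug, so that each is rated under E(6).
- **E(8):** use the same object as E(6).
- **E(7):** add the relatedness rating to the adverse event log fields.
- **Minor, E(6):** state that Related and Possibly Related both count as related.

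The cost is amended wording in four subsections and slightly more adjudication work. No visits, tests or subjects are added, and clinical management does not change.

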The PI and delegates are responsible for notifying the DSMB chair of all SAEs. DSMB panel will evaluate the relationship of the SAE to the underlying disease. The PI, in cooperation with the DSMB panel, will determine whether the SAE is unexpected in nature and make a recommendation for any further action. The primary consideration is the study subjects' safety.

(8) Regulatory Reporting

The PI will report events that are both serious and unexpected and that are associated with Study Agent/Intervention to the FDA and other applicable health authorities within the required timelines as specified in 21 CFR 312.32: fatal and life threatening events within 7 calendar days (by phone /fax/electronic communication) and all other serious adverse events in writing within 15 calendar days. All serious events designed as "not associated" to Study Agent/Intervention, will be reported to the FDA at least annually.

Given the low dose and method of delivery of fluorescein sodium, serious adverse events related to the study drug are not anticipated. Subjects will be monitored at the time of dye application to observe for signs of allergy or intolerance. If any signs of allergy or intolerance occur (as evidenced by discoloration of tissue or other signs of allergic reaction), the dye will be immediately flushed out and no images will be obtained. As per standard of care for patients undergoing cardiac surgery, subjects will receive an intraoperative echocardiogram after being separated from bypass, and will be monitored closely post-surgery. Before being discharged, all subjects will receive an electrocardiogram and trans-thoracic echocardiogram, in accordance with standard of care.

F. Data Management Methods

Study specific case report forms (CRFs) will be completed and the case report forms will be stored in individual subject binders. Data will be transcribed to a secure research data management system (InForm database). All hardcopies will be kept in a locked file cabinet accessible by authorized study staff only. Subject confidentiality will be maintained by recording subject data using a unique subject identifier. Identifiable linking data, such as contact information and medical record numbers, will be recorded and stored separately from the clinical study data.

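### DSMB review is a condition of the next enrolment for three rhythm/pressor events only; for SAEs it is required but untimed and not tied to enrolment, and non-serious myocarditis or dye reactions have no stated DSMB route

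*Protocol*

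**What the plan says.** **Events that hold enrolment.** Section E(6) of the protocol has a short list headed "Specific ECG and rhythm abnormalities requiring DSMB review prior to enrollment of next patient". Its items are:

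1. "AV block > the a PR interval > 220 msec lasting more than 2 hours post completion of cardiopulmonary bypass" (with an exception for certain transient block);
2. pacing of the atrium, or a junctional rhythm, that goes on for over 6 hours after the procedure;
3. a haemodynamic trigger, worded as "Hypotension or ventricular dysfunction requiring pressor support > 5mcg/kg/min of dopamine more than 4 hours post completion of cardiopulmonary bypass".

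No other section of the protocol makes enrolment wait for anything.

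**Serious adverse events.** Section E(3) defines these and includes death and life-threatening events. Section E(7) states: "The PI and delegates are responsible for notifying the DSMB chair of all SAEs". It continues: "DSMB panel will evaluate the relationship of the SAE to the underlying disease". The investigator and the panel then decide whether the event was unexpected and recommend any further action. SAEs also go promptly to the IRB. No time is set for the notice to the chair or for the panel's evaluation.

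**Events pre-declared related or possibly related.** E(6) names "myocarditis or ventricular dysfunction, as measured by ejection fraction and fractional shortening" and sends these to the FDA in an IND safety report. The DSMB is not mentioned for them at that point.

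**Dye reactions.** Sections D(1) and E(8) say that on signs of allergy or intolerance the dye is flushed out and imaging is not done. Neither mentions the DSMB or the next subject.

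**FDA reporting.** For events that are serious, unexpected and associated with the study agent, E(8) requires reporting of "fatal and life threatening events within 7 calendar days" and of other serious events within 15.

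**The concern.** The primary aim is the safety of the dye during cardiac surgery. The cardiac experience that the protocol describes is in rats and three sheep, and subjects may be as young as 30 days. With six subjects and no comparison group, a look at each patient's course before the next is enrolled is an important protection. The protocol accepts that principle for three events.

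The difficulty is which events are covered. Followed literally, a PR interval above the limit for more than two hours stops the next enrolment until the DSMB has looked. A death, a life-threatening event, myocarditis or a dye reaction does not, unless it also produces one of the three listed triggers. At stake is whether another child is exposed while an unreviewed serious or dye-related event is outstanding. The hold rule is a conduct rule that the protocol itself fixes, so this is not detail that would ordinarily be left to a statistical analysis plan.

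**Working it through.** The protocol gives no stopping boundary or event-count rule to reproduce. The check is to trace each kind of event through the document and then to bound the exposure.

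**Step 1. Trace each event.**

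| Event | On the E(6) hold list? | Stated DSMB step | Is enrolment said to wait? |
|---|---|---|---|
| PR prolongation / AV block over 2 hours | Yes | Review before next patient | Yes |
| Atrial pacing or junctional rhythm over 6 hours | Yes | Review before next patient | Yes |
| Hypotension or ventricular dysfunction meeting the pressor criterion | Yes | Review before next patient | Yes |
| Death or life-threatening event | No | Chair notified, panel evaluates, recommendation made (E(7)); untimed | No |
| Any other SAE | No | Same as above | No |
| Ventricular dysfunction below the pressor criterion | No | Only if serious | No |
| Myocarditis | No | Only if serious | No |
| Dye reaction with flushing | No | Only if serious | No |

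An event in the lower five rows holds enrolment only if it also produces one of the three listed triggers.

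**Step 2. Look for another provision that closes the gap.**
- The FDA timelines in E(8) apply only to events that are serious, unexpected and associated. They do not time the DSMB's work and do not stop enrolment.
- Prompt IRB reporting in E(7) is not tied to the next enrolment.
- Sections G and H mention a manual of operations and a Monitoring Plan, but the protocol does not point to either for a pause.
- No minimum interval between subjects is stated.

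**Step 3. Bound the exposure.** Inputs: six subjects (D(1)); recruitment, enrolment and follow-up within six months, with several patients eligible weekly (D(6)). The actual enrolment pace is not given. The 7- and 15-day intervals serve only as a yardstick, because no DSMB interval is stated.

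*Lower end.* Six subjects spread evenly over six months, taken as 26 weeks:
- pace = 6 / 26 = 0.23 per week
- in 7 days: 0.23 × 7/7 ≈ 0.2 subjects
- in 15 days: 0.23 × 15/7 ≈ 0.5 subjects

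*Upper end.* Assume that several means 2 to 4 eligible per week:
- in 7 days: 2 to 4 eligible
- in 15 days: 2 × 15/7 = 4.3 to 4 × 15/7 = 8.6 eligible

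If the event is in the first subject, five remain. At 4 eligible per week, all five could be enrolled within 15 days if 5 / 8.6 = 58% of eligible patients enrolled. At 2 per week, 4.3 is below five, so even full uptake would not quite reach it. All five is therefore an upper bound, not an expectation.

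**The case against.** The strongest reply is that the E(6) list is an additional layer. It brings to the DSMB some rhythm and pressor events that might not count as serious, while SAEs have their own route in E(7), where subject safety is said to come first. On that reading the two sections do not contradict each other, and nothing in the text authorises enrolment while a recommendation is pending. One person also gives all the dye and takes all the images (section K), so a reaction in theatre would be known to the operator before the next case. In practice the team would probably pause after a death.

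Much of this stands:
- A reader might infer that a death or life-threatening event escapes the DSMB. It does not: E(7) requires notification, evaluation and a recommendation for every SAE. What is missing is the order and the timing.
- A reader might infer that the sections conflict. They leave a gap.
- Ventricular dysfunction is not simply omitted, since the third trigger covers the part that meets the pressor criterion. A dye reaction with hypotension could reach that trigger too.
- Eligible patients are not enrolled patients. Consent of both parents (or self-consent at 18 to 21) and the exclusions reduce the number.
- Holding enrolment for every related event of any grade would be a broad rule, and the documents do not require it.

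What the reply does not remove is that the protocol states a wait explicitly for three events and is silent on it for SAEs, and that non-serious myocarditis and non-serious dye reactions have no stated DSMB step. A manual or DSMB charter might add a pause, but none is cited for that purpose.

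**Conclusion.** The point holds as a gap in the hold rule. For SAEs the DSMB's evaluation is required but is neither timed nor made a condition of the next enrolment. Myocarditis and dye-flush cases reach the DSMB only if they are serious or meet a listed trigger, and ventricular dysfunction holds enrolment only through the pressor criterion. The next subject could therefore be enrolled after such an event before DSMB review, while a less severe PR prolongation would hold enrolment.

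The likely exposure is modest at an even pace, about 0.2 to 0.5 subjects over 7 to 15 days. The upper bound of all five remaining subjects needs an event in the first subject, a flow near the top of the assumed 2 to 4 eligible per week, and enrolment of most of them. A reader might infer that all five would be enrolled before any report is due. The documents do not support that: SAEs go promptly to the IRB, and the FDA periods do not govern DSMB review. The gap itself does not depend on the pace. The conclusion rests on the protocol alone and would be met if a referenced document already contained the pause.

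**What to change.** Bring E(6) and E(7) into line:

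- State in E(7) that enrolment of the next patient waits for the DSMB evaluation and recommendation already required for SAEs.
- Set a time for notifying the chair.
- Give a stated DSMB route to the events that E(6) pre-declares as related or possibly related, and to cases in which the dye is flushed for suspected allergy or intolerance.
- Record whether the hold also applies to those events when they are not serious. That choice, and any threshold, belongs to the sponsor and the DSMB; none is proposed here.
- If a pause rule already exists in the manual of operations or a DSMB charter, cite it in the protocol.

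The change is a few sentences and uses the existing DSMB and the protocol's own event categories. The cost is a possible short pause in enrolment. It would be longer if the sponsor chose to include non-serious events, or if SAEs arose from common complications of the operation, such as a prolonged stay.

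### E(4) labels listed ASD-repair complications, rhythm events included, expected and unrelated in advance; a study-caused conduction injury then moves from expedited to annual FDA reporting, and if judged associated but expected it has no stated route

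*Protocol*

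**What the plan says.** **E(8), Regulatory Reporting**, sets two FDA routes for serious events.
- Expedited: "events that are both serious and unexpected and that are associated with Study Agent/Intervention to the FDA", with "fatal and life threatening events within 7 calendar days" and other serious events within 15.
- Periodic: serious events designated as not associated with the agent or intervention, which "will be reported to the FDA at least annually".

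**E(4), Definition of Unexpected Adverse Events**, gives two tests.
- An event is unexpected "when its nature (specificity) or severity is not consistent with applicable product information", or with the investigational plan, brochure or protocol.
- It is also unexpected "when not one of the most common complications that typically arise post-operation for ASD repair". The examples are "rhythm disturbances, arrhythmia, pericarditis, cardiac tamponade, bleeding, residual holes requiring a re-operation, transfusion associated diseases, stroke, and brain damage". The section closes by classing these complications as both expected and not related to the study drug.

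**E(6), Guidelines for Determining Causality**, requires a relationship assessment for every adverse event and says the product is always to be suspected. It sends myocarditis and ventricular dysfunction to the FDA in an IND Safety Report and states no expectedness condition. It also requires DSMB review before the next enrolment for specified AV block, pacing or junctional rhythm, and hypotension or ventricular dysfunction needing pressor support.

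**E(7), Recording and Reporting Procedures**, sends SAEs promptly to the IRB and all SAEs to the DSMB chair. The PI, with the DSMB, decides whether an SAE is unexpected in nature.

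**The concern.** The study's primary aim is safety (section A). The background (section B) presents complete heart block from damaged conductive tissue as the surgical complication that motivates the work. Section D(2) chooses ASD repair because it exposes the conduction system, and section D(1) puts dye on the myocardium and a probe in direct contact with it for about 90 seconds. A conduction injury is therefore a harm that the study could plausibly cause.

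Yet rhythm disturbances and arrhythmia head the list that E(4) settles in advance. Both labels on that list, expected and unrelated, take an event out of expedited reporting, whatever its severity and whatever an individual assessment might find. What is at stake is whether the FDA learns promptly, and with an honest causality label, of a serious study-caused event under the IND.

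**Working it through.** No sample size, rate or error probability bears on this point, so the check sets the rules side by side.

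**Step 1. FDA routes in E(8) for a serious event**

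| | Unexpected | Expected |
|---|---|---|
| Associated | 7 or 15 days | no route stated |
| Not associated | at least annually | at least annually |

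One of the four cells is empty.

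**Step 2. Other FDA routes.** E(6) covers myocarditis and ventricular dysfunction only. Section G sends the FDA significant protocol deviations, not adverse events. Neither fills the empty cell for a rhythm event.

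**Step 3. Place a serious conduction injury in the table.** Take a permanent heart block caused by dye or probe. Heart block is not named in E(4); I assume that it falls under rhythm disturbances. Three readings are open.

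- *(A) E(4)'s closing sentence applied as written.* The event is expected and unrelated, hence not associated. It goes to the FDA at least annually, labelled unrelated.
- *(B) Judged associated, but kept as expected because it is listed.* The event falls in the empty cell.
- *(C) Judged associated, and unexpected by E(4)'s first test or by the PI with the DSMB.* The 7- or 15-day route applies.

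**Step 4. Is (B) reachable?** Yes, in two ways. First, E(4) declares the listed events unrelated to the *drug*, whereas E(8) asks about association with the agent *or intervention*. A block attributed to probe contact can thus be associated under E(8) while E(4) still calls it expected. Second, an investigator who follows E(6) and finds the event related sets aside only the unrelated label; nothing in the text says that the expected label falls with it. A finding of relatedness then moves the event from the annual report to no stated FDA route.

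**Step 5. What (A) costs in time.** An annual interval can be up to 365 days. Against the expedited limits, the delay could reach 365 − 15 = 350 days, or 365 − 7 = 358 days for a life-threatening event. Section D(6) expects recruitment, enrolment and follow-up to finish within 6 months of activation, so an annual report could arrive after all six subjects have been treated.

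**Step 6. The internal conflicts.** E(4)'s first test makes severity count and its list does not. E(4) settles relatedness by category, while E(6) requires it event by event.

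**The case against.** The strongest reply is that the list attaches both labels together. A listed serious event is therefore not associated by default, and E(8) does report such events annually. This stands. A reader might infer from the empty cell that a study-caused heart block would never reach the FDA, or that every listed complication lacks a route. The documents do not support either: no route is missing unless the unrelated label is overridden and the expected label is kept. Some listed items, such as residual holes or transfusion-associated disease, are in any case poor candidates for attribution to dye or probe.

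Second, E(4)'s list test opens as an addition to the first, so either test alone may be enough to make an event unexpected. The dye reactions described in section C do not include conduction injury, so the first test could make a heart block unexpected. The PI and DSMB also decide expectedness for each SAE. This stands in part, because reading (C) is available. But it requires setting aside E(4)'s categorical closing sentence. E(7) also asks only whether the SAE is unexpected in nature, and puts to the DSMB the relation to the underlying disease, not to the imaging.

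Third, the safeguards are real. All SAEs go to the DSMB chair, SAEs go promptly to the IRB, and AV block or pacing need beyond the stated limits requires DSMB review before the next enrolment. This stands, and it confines the gap to FDA reporting.

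**Conclusion.** The point holds in this form: E(4)'s advance classification conflicts with its own first test and with E(6). It diverts a serious study-caused rhythm event from 7/15-day reporting to an annual report that calls it unrelated. In the narrower case of an event judged associated but expected, E(8) states no FDA route. That is one of four combinations.

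This rests on two assumptions: that conduction injury counts as a rhythm disturbance under E(4), and that E(4)'s closing sentence is applied as it reads. Under a different reading of E(4) the event would be expedited, so the plan is ambiguous and does not uniformly fail. It is still more than a missing detail, because a stated rule fixes the classification of events that a safety study needs to assess individually. The sponsor should correct it.

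**What to change.** - **E(4):** delete the sentence that classes the listed complications as expected and unrelated. Judge expectedness by one test, nature and severity against the dye and device safety information. Keep the ASD-repair list only as background for interpreting complication rates.
- **E(6):** assess relatedness event by event, for the imaging procedure as well as the drug, with no category exempted.
- **E(8):** send every serious associated event to the FDA, expedited if unexpected and otherwise in the annual report alongside the not-associated events.

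The cost is protocol wording and possibly one or two additional expedited reports in a six-subject study. The DSMB and IRB routes stay as they are.
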